#### 4. Study Endpoints

## PRIMARY ENDPOINTS

1. To determine whether informing clinicians of the SSCVD test results leads to changes in prescriptions and/or medical management of participants with T2D in concordance with SSCVD results over a 6-month period (Informed arm) when compared to participants whose physicians are not informed of the test results (Uninformed arm).

## SECONDARY ENDPOINTS

1. To evaluate longitudinal changes in the (i) SSCVD results and (ii) conventional risk factors over 6 months in participants whose clinicians were informed vs. those whose clinicians were uninformed of the SSCVD results.
2. To determine whether changes in the SSCVD score and conventional risk factors over 6 months relate to (i) baseline SSCVD risk category group and (ii) changes in treatment.
3. To enable future health economic analyses of the impact of precision risk-stratified treatment.
4. To determine whether provision of the SSCVD test along with the SomaLogic Metabolic Factors panel with 8 test results that reflect changes in: Liver Fat, Glucose Tolerance, Alcohol Impact, Cardiorespiratory Fitness/VO2 max, Resting Energy Rate, Body Fat Percentage, Visceral Fat, Lean Body Mass to physicians whose participants are randomized to the Uninformed group after 6 months results in changes in participant management.

### **Outcome Measurements:**

The following measurements will be made at baseline and after 6 (+/-1 months).

#### **Primary Aim**

Changes in prescription medications and lifestyle interventions

[figure not shown]
#### **Secondary Aims:**

- (i) SSCVD test results at baseline and 6 months;
- (ii) change in CVD risk factors measured using laboratory assessments (Complete Blood Count (CBC), Basic Metabolic Panel (BMP), Hemoglobin A1C, Lipid panel), anthropometric measurements (height, weight and BMI), lifestyle/behavioral changes (smoking, diet and exercise) measured using questionnaires.
- (iii) Physician experience questionnaire
- (iv) Participant adherence: to their medications will be quantified using the medication possession ratio (# of scripts filled/# of months participants are script eligible).

Blood will be frozen at -80 degrees C for future evaluation of biomarkers including metabolites and micro RNAs.

## 5. Study Intervention

**Figure 1:**

All participating providers will be provided education and training on SomaSignal testing including how to interpret and educate participants on the results. The documents used in this training are included in Appendix A.

#### **Enrolment and Randomization:**

Eligible participants based on the inclusion/exclusion criteria will provide written informed consent.

All participants in the Informed arm will be provided SSCVD test information. The Uninformed arm will receive both the SSCVD and SomaSignal Metabolic Factor test information at the end of 6 months.

Participants will be randomized to one of 2 arms of the study. Randomization will be stratified based upon the presence on CVD.

Treatment Arm	Intervention
Arm 1: (SSCVD Informed)  SomaSignal Informed Medical Management SSCVD	Blood draw for SSCVD test at baseline and 6 months ( $\pm 50$ days).  SSCVD results will be sent to the providers and participants approximately 2-4 weeks after testing.  Participants visit or are contacted by their physician up to 50 days after baseline testing to discuss treatment strategy (no changes, add/remove medications, lifestyle intervention, etc.)

	
Medical records will be reviewed by the study team to evaluate changes in treatment strategy.
 
Participants will be called 2 weeks, 2 months, and 4 months (+/- 7 days) after the baseline visit to ask if they are following the treatment strategy.

Arm 2: (SSCVD Uninformed) Standard of Care where the provider is not informed of the SSCVD test results	
Blood draw for SSCVD test at baseline and 6 months (<math>\pm 50</math> days). SSCVD results will not be provided to the provider or participant until the 6-month visit.
 
Participants visit or are contacted by their physician up to 50 days after baseline testing to discuss treatment strategy (no changes, add/remove medications, lifestyle intervention, etc.)
 
Medical records will be reviewed by the study team to evaluate changes in treatment strategy.
 
Participants will be called 2 weeks, 2 months, and 4 months (+/- 7 days) after the baseline visit to ask if they are following the treatment strategy.
 
After the 6-month period is completed, the providers will discuss results of the SSCVD and SomaSignal Metabolic Factor tests (obtained during the Baseline and 6-month blood draws) with the participant and make any adjustments to the care plan as needed.
 
Medical records will be reviewed by the study team to evaluate changes in treatment strategy.

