## 2. Objectives

### Primary Aim:

1. To determine whether informing clinicians of the SSCVD test results leads to changes in prescriptions and/or medical management of participants with T2D in concordance with SSCVD results over a 6-month period (Informed arm) when compared to participants whose treatment is not informed by SSCVD test results (Uninformed arm).

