## 6. Procedures Involved

**Blood Draws:** Blood samples (45 ml) will be collected either at an Emory or Grady site from participants in both arms of the study at Baseline and after 6 months (+/- 50 days) for the SSCVD test and CVD risk factors measured using laboratory assessments (Complete Blood Count (CBC), Basic Metabolic Panel (BMP), Hemoglobin A1C, Lipid panel).

Blood samples for the SomaSignal tests will be shipped to SomaLogic for analysis and the results will be delivered to Emory using secure electronic means. Remaining blood will be frozen at -80 degrees C and stored at Emory for future evaluation of biomarkers including metabolites and micro RNAs.

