**Informed Arm:**

For participants randomized to the Informed arm, the SSCVD test results will be provided to the participant's clinicians approximately 2-4 weeks after the baseline blood draw.

Clinicians will discuss results with the participant and make adjustments to the care plan as needed based on the SSCVD test results within 50 days of receiving results. Clinicians may advise participants to (i) either change the doses of existing medications within existing guidelines, (ii) prescribe additional guideline-based medications, (iii) advise additional lifestyle interventions, or (iv) advise no change. This information will be documented in the case report forms.

This test is neither intended to diagnose cardiovascular disease (CVD) nor replace standard of care protocols for this disease. The physician should not rely solely on this information to make a decision on the best course of action for this patient.

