**Uninformed Arm:**

Clinicians will provide standard of care based on routine test results and without the SSCVD results.

SSCVD and SomaSignal Metabolic Factor Panel results from participants from both the baseline and 6-month period will be provided to the study team at the 6-month study visit.

The SomaSignal Metabolic Factor tests include evaluation of Liver Fat, Glucose Tolerance, Alcohol Impact, Cardiorespiratory Fitness/VO2 max, Resting Energy Rate, Body Fat Percentage, Visceral Fat, and Lean Body Mass.

Any recommendations made to the participant by the physicians, based on obtaining the aforementioned test results will be collected.

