## **23. Resources Available**

A Clinical Research Coordinator will be allocated to recruit participants and conduct study procedures. He/she will be assisted by Cardiology Research Fellows. Other study staff will assist with the identification of potential participants, chart review and data entry. The study team has approximately 800 square feet of dedicated research space in 5 rooms in the Woodruff Memorial Research Building (WMB) with 3 beds and 2 recliners available. In Emory University Hospital (EUH), there are 2 research exam rooms and 3 offices available to conduct study visits.

It is not anticipated that additional medical services will be needed as a result of the research. If necessary EUH is a state-of-the-art, acute-care hospital that includes cardiac care, surgery, and 24/7 emergency services. The WMB is directly adjacent to EUH and is equipped with defibrillators. Additionally, study staff are trained in Basic Life Support.

All study staff will be trained on the protocol prior to study initiation. Documentation of training and qualifications will be maintained in the study regulatory binders. The Research Manager will oversee the day-to-day activities of the coordinators/study nurses and other members of the study staff. The PI meets regularly with all personnel to review the progress of the study and communicate with them as needed to monitor adverse events and provide timely updates on changes to the protocol or procedures.

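### The study team evaluates treatment changes for the primary outcome from charts, and the protocol does not mask that step; fact-only abstraction with classification blind to arm would reduce the risk of bias

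*Protocol*

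**What the plan says.** The primary aim (Protocol Sections 1, 2 and 4) compares the arms on changes in prescriptions or medical management over 6 months that agree with the SSCVD result. Under Outcome Measurements in Section 4, the primary measurement is "Changes in prescription medications and lifestyle interventions"; a figure that follows it is not shown.

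- **Who assesses.** The arm table in Section 5 states for both arms: "Medical records will be reviewed by the study team to evaluate changes in treatment strategy". Section 6, Medical Record Review, runs the abstraction from baseline to the 6-month visit.
- **What counts as management.** Section 6, Informed Arm, lists dose changes, added drugs, lifestyle advice and no change. The clinician's decision is to go on the case report form. The Uninformed Arm text has no matching sentence for the 6-month period, but the Section 9 schedule lists treatment changes and reasons without distinguishing the arms.
- **Release of results, Informed arm.** Section 6 says "the SSCVD test results will be provided to the participant's clinicians approximately 2-4 weeks after the baseline blood draw". Section 5 adds participants as recipients.
- **Release of results, Uninformed arm.** SSCVD and metabolic panel "results from participants from both the baseline and 6-month period will be provided to the study team at the 6-month study visit".
- **Route.** For all SomaSignal samples, "the results will be delivered to Emory using secure electronic means".
- **Staff.** Section 23: "Other study staff will assist with the identification of potential participants, chart review and data entry".

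No section describes masking of the chart reviewer, an independent assessor, or a separation between staff who handle results and staff who review charts.

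**The concern.** Evaluating a change in treatment strategy asks more of a reviewer than copying facts. A new drug with a start date leaves little room for opinion. Whether a note about diet and exercise counts as a lifestyle intervention, or a small dose adjustment counts as a change of strategy, leaves more. The overarching hypothesis in Section 3 expects more added therapy at high than at low residual risk, so the same event can count differently by risk category.

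If reviewers know the arm, these softer items may be found or coded more readily in one arm than in the other. The primary comparison would then mix a real effect on prescribing with a difference in how charts were read. An analysis plan cannot repair this afterwards, because it would receive items already judged by unmasked staff. Who abstracts, what they record and what they can see are matters of conduct that Sections 5 and 6 already address.

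**Working it through.** **What the text establishes**

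1. *Is the reviewer masked?* Section 5 names the study team in both arms and no section masks it. Section 18 gives the Emory study team and the sponsor access to the database, with no restriction by arm or result described.
2. *Does the reviewer know the arm?* This is not stated in words. However, the team receives results and the metabolic panel for Uninformed participants at the 6-month visit, and only that arm enters the extension. By the end of the primary period the arm is therefore evident to the team.
3. *Is knowledge of the SSCVD result unequal?* The protocol states only that the team gets Uninformed results at 6 months. In the Informed arm the named recipients are clinicians and participants. By the 6-month visit results are available in both arms.
4. *Can primary and extension changes be confused?* In the Uninformed arm Section 5 provides for a further record review after disclosure. Section 9 puts the extension and the closing record of treatment changes in the same Final Study Visit column. Only dates separate the two.

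**Illustration of size**

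The protocol gives no effect size, background rate, alpha or allocation ratio for the primary outcome, so there is no figure to reproduce. The total of 450 comes from Sections 1 and 12. Assumed: 1:1 allocation (225 per arm), a two-sided 5% test, and no true difference.

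With recorded rates p1 (Informed) and p2 (Uninformed), d = p1 − p2 and p̄ = (p1 + p2)/2:

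- SE0 = √(2·p̄(1 − p̄)/225)
- SE1 = √((p1(1 − p1) + p2(1 − p2))/225)
- c = 1.96·SE0
- Rejection rate = [1 − Φ((c − d)/SE1)] + Φ((−c − d)/SE1)

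For 35% against 30%: SE0 = √(2 × 0.325 × 0.675/225) = 0.0442, c = 0.0866, SE1 = √((0.2275 + 0.21)/225) = 0.0441. Upper tail: 1 − Φ(0.829) = 0.204. Lower tail: about 0.001. Total 0.205.

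For 40% against 30%: SE0 = 0.0450, c = 0.0881, SE1 = √((0.24 + 0.21)/225) = 0.0447. Total 1 − Φ(−0.265) = 0.605.

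The same formula over a range of assumed base rates gives these false-positive rates:

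| Spurious excess | Base 10% | Base 15% | Base 30% | Base 50% |
|---|---|---|---|---|
| 0 points | 5% | 5% | 5% | 5% |
| 3 points | 16.9% | 13.7% | 10.5% | 9.7% |
| 5 points | 36.1% | 28.6% | 20.5% | 18.6% |
| 10 points | 84.6% | 75.7% | 60.5% | 56.9% |

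Five points is 0.05 × 225 = 11.25, about 11 participants in one arm.

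Unequal capture of real changes can be treated in the same way. Suppose 95% of changes are captured in one arm and 80% in the other. At a true rate of 30% the recorded rates are 0.95 × 0.30 = 28.5% and 0.80 × 0.30 = 24.0%, and the false-positive rate is 19.2%. At true rates of 15% and 50% it is 10.9% and 36.1%.

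For scale, the true difference detectable with 80% power at 225 per arm is 9.3, 10.6, 12.7 and 13.1 points at base rates of 10%, 15%, 30% and 50%.

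**The case against.** The strongest reply has five parts.

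- **Unequal knowledge of the result.** A reader might infer that the team learns Informed results at 2–4 weeks and so knows the SSCVD result during follow-up in that arm only. The text does not say this: Informed results go to clinicians and participants, and delivery to Emory is described for all samples alike. Concordance also cannot be judged without the result, which by 6 months is available in both arms. This objection stands. The point rests on unmasked review and knowledge of the arm.
- **A rule may already exist.** No section says that a reviewer decides concordance. A rule may sit in the figure that is not shown or in an analysis plan. This stands too, and the absence of a rule is not claimed. A rule would still take its inputs from unmasked review.
- **Other sources.** Case report forms, questionnaires and the scheduled record of treatment changes supplement the chart. This is true, and the fix should cover them. None of them is described as masked.
- **The remedy is partial.** Abstractors may see the test mentioned in Informed charts, and informed clinicians may chart more fully. This stands.
- **The numbers are assumed.** They are. The nearest figures in Section 3 are uptake below 10% and drop-in of 11.7% to 14.8%, neither of which is the primary outcome. The direction of any bias is not established by the protocol either; sponsor funding does not show how institutional staff would code a chart.

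**Conclusion.** The point holds in limited form. The primary outcome relies in both arms on an evaluation of charts by the study team, the protocol does not mask that step, and the arm is evident to the team by the 6-month visit. Lifestyle advice and dose changes are the exposed items; new prescriptions are much less so.

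The documents do not support the stronger readings that the team is shown to see Informed results early, that the concordance call is made with unequal knowledge of the result, or that masking would eliminate the bias.

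The size is unknown. With 225 per arm, a 30% rate in both arms and a two-sided 5% test, all assumed, an excess of 5 or 10 points from coding alone would raise the false-positive rate to about 20% or 60%. The change is worth making because it is inexpensive and protects the primary comparison.

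**What to change.** In Sections 5 and 6:

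1. Limit the study team to abstracting dated facts from charts and case report forms: drug, dose, start or stop date, and documented lifestyle advice or referral. Use the same form and the same time window in both arms.
2. Classify change and concordance by the prespecified rule, in the analysis plan if it is there. Run it on those facts plus the baseline SSCVD category, with the arm label hidden.
3. Exclude by date any Uninformed-arm change made after disclosure, so that extension changes cannot enter the primary outcome.

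The cost is a common abstraction form and a short program. The chart-review staff listed in Section 23 are enough, and no extra assessor is needed. Some free-text nuance is lost. Keeping documented lifestyle advice on the form, and not referrals alone, avoids narrowing the outcome. A sentence acknowledging that Informed charts may reveal the test, and may be fuller, would state the remaining limit.

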## 6. Procedures Involved

**Blood Draws:** Blood samples (45 ml) will be collected either at an Emory or Grady site from participants in both arms of the study at Baseline and after 6 months (+/- 50 days) for the SSCVD test and CVD risk factors measured using laboratory assessments (Complete Blood Count (CBC), Basic Metabolic Panel (BMP), Hemoglobin A1C, Lipid panel).

Blood samples for the SomaSignal tests will be shipped to SomaLogic for analysis and the results will be delivered to Emory using secure electronic means. Remaining blood will be frozen at -80 degrees C and stored at Emory for future evaluation of biomarkers including metabolites and micro RNAs.

### **Vital Signs**

Participants in both arms of the study will have their vital signs taken and recorded at their Baseline and 6 month visits.

### **Questionnaires**

Participants will be asked about their medications, family and medical history, and lifestyle. These questionnaires may be administered in person or online via REDCap.

### **Medical Record Review**

Clinical Data Abstraction will occur from the baseline visit to the 6-month (+/- 50 days) study visit.

### **Phone Visit**

Participants will be called 2 weeks, 2 months, and 4 months (+/- 7 days) after the baseline visit to ask if they are following the treatment strategy.

### **Clinician Intervention/s:**

All participating clinicians will be educated through materials and webinars provided by SomaLogic.

**Informed Arm:**

For participants randomized to the Informed arm, the SSCVD test results will be provided to the participant's clinicians approximately 2-4 weeks after the baseline blood draw.

Clinicians will discuss results with the participant and make adjustments to the care plan as needed based on the SSCVD test results within 50 days of receiving results. Clinicians may advise participants to (i) either change the doses of existing medications within existing guidelines, (ii) prescribe additional guideline-based medications, (iii) advise additional lifestyle interventions, or (iv) advise no change. This information will be documented in the case report forms.

This test is neither intended to diagnose cardiovascular disease (CVD) nor replace standard of care protocols for this disease. The physician should not rely solely on this information to make a decision on the best course of action for this patient.

**Uninformed Arm:**

Clinicians will provide standard of care based on routine test results and without the SSCVD results.

SSCVD and SomaSignal Metabolic Factor Panel results from participants from both the baseline and 6-month period will be provided to the study team at the 6-month study visit.

The SomaSignal Metabolic Factor tests include evaluation of Liver Fat, Glucose Tolerance, Alcohol Impact, Cardiorespiratory Fitness/VO2 max, Resting Energy Rate, Body Fat Percentage, Visceral Fat, and Lean Body Mass.

Any recommendations made to the participant by the physicians, based on obtaining the aforementioned test results will be collected.

## **7. Data Specimen Banking**

Data obtained from this study will be shared with SomaLogic, Inc. as per the clinical research data sharing agreement that will be developed as a separate document, prior to the start of this study. If applicable, all shared data and/or biological samples will be de-identified as per the Privacy Rule of the NIH (National Institutes of Health, 2007) and in accordance with Emory policies.

In the event that SomaLogic, Inc. performs similar studies with other institutions, the data obtained during this study may be combined for internal future studies or a meta-analysis as appropriate. Data generated as part of this study will not be shared outside Emory and SomaLogic, Inc., unless expressly agreed to in writing and with the proper regulatory and contractual approvals.

Blood will be frozen at -80 degrees C and stored at in secure freezers in the Woodruff Memorial Research Building for future evaluation by Emory investigators of biomarkers including metabolites and micro RNAs.

All specimens and data will be identified with a study ID number. Direct identifiers will not be attached to any records or samples. Study data will be kept in a secure storage area or password-protected database. Access to this database will be restricted by a database manager. Only those members of the study staff listed on the delegation of authority log will have access to identifiers.

De-identified study data and specimens may be shared with Emory and non-Emory investigators to help them study cardiovascular diseases. Any future use of data and specimens for research must be authorized by the Principal Investigator and approved by an Institutional Review Board. The research investigators involved in this study and in future studies and any other individual who may have access to the blood sample and its derivatives are not authorized to and are forever prohibited from using this material for any attempt at cloning a human being.

Information that may be released to researchers may include, but is not limited to: medical information, age, gender, ethnic background, family history, imaging data, blood samples and blood sample products. Identifiers, like names, addresses, and social security numbers, will not be released, except if patients need to be contacted again for specific purposes in new studies. All efforts will be made to keep identifying information confidential.

## **8. Sharing of Results with Participants**

Clinicians in both arms of the study will receive results of participants' routine lab tests and will share them with participants.

## 9. Study Timelines

Event	Screening and Blood Draw 1 (Baseline - 1month)	Baseline Visit	Phone Visit 2 weeks, 2 months, 4 months	Blood Draw 2 + 6 months after Baseline Visit	Final Study Visit
Informed Consent	X				
Inclusion/Exclusion Criteria	X				
Medical History	X				
Standard of Care Visit		X			X
Vital signs/exam	X				
Review of Medical Record/Concomitant Medications*	X	X		X	X
Questionnaires	X		X		X
Laboratory Tests-CBC, BMP, Hb A1C, Lipid panel	X			X	
SomaSignal Test (blood draw)	X			X	
Treatment changes and reasons		X			X
Open Label Extension					X 

only for the Uninformed group

\*Review of Medical Record including concomitant medications will occur during the course of the study

